# 5.1.3. Hoehn and Yahr Stage

The Hoehn and Yahr is a commonly used system for describing how the symptoms of PD progress. The scale allocates stages from 0 to 5 to indicate the relative level of disability. This scale is included within the MDS-UPDRS and will be completed for all subjects.

- Stage zero: No symptoms.
- Stage one: Symptoms on one side of the body only.
- Stage two: Symptoms on both sides of the body. No impairment of balance.

• Stage three: Balance impairment. Mild to moderate disease. Physically independent.

- Stage four: Severe disability, but still able to walk or stand unassisted.
- Stage five: Wheelchair-bound or bedridden unless assisted.

## 5.1.4. Modified Schwab and England (PD Subjects Only)

The Modified Schwab and England ADL scale reflects the speed, ease, and independence with which an individual performs daily activities, or personal chores, such as eating, toileting, and dressing. This scale uses a rating scale from 0% to 100%, with 100% representing complete independence in performing daily activities and 0% representing a vegetative, bedridden state.

## 5.1.5. Scales for Outcomes in Parkinson's Disease (SCOPA-AUT)

The SCOPA-AUT is a 26-item self-administered test developed to evaluate autonomic symptoms, such as GI and urinary problems, in subjects with PD.

## 5.1.6. University of Pennsylvania Smell Identification Test (UPSIT)

Odor identification performance will be assessed using the UPSIT (Doty et al, 1995), which will be self-administered at the Screening Visit. The UPSIT is a standardized, four-alternative, forced-choice test comprised of four booklets containing ten odorants apiece, one odorant per page. The stimuli are embedded in "scratch and sniff" microcapsules fixed and positioned on strips at the bottom of each page. A multiple-choice question with four-response alternative for each item is located above each odorant strip. Raw scores are calculated as the number of correct identifications. A percentile will be assigned based on comparison with age and gender matched controls.

## 5.1.7. The Montreal Cognitive Assessment (MoCA)

The MOCA was designed as a rapid screening instrument for mild cognitive dysfunction. It assesses different cognitive domains: attention and concentration, executive functions, memory, Protocol No.: S4-001v4.0 Date: 18 October 2016 Page 28 of 54 language, visuoconstructional skills, conceptual thinking, calculations, and orientation. Time to administer the MoCA is approximately 10 minutes. The total possible score is 30 points; a score of 26 or above is considered normal. This scale will be performed at the clinical site as part of the baseline clinical characterization.

### 5.1.8. **Dopamine Transporter Imaging**

Subjects will have DAT imaging procedure to measure the amount of dopamine in the brain using SPECT. All subjects will undergo SPECT imaging as part of the screening.

The SPECT imaging procedure will be performed at the individual sites using DaTSCANTM.

Upon completion of the initial (Screening) SPECT scan, the imaging core will complete a Visual Interpretation Report. For PD subjects, the Visual Interpretation Report will be provided to the clinical site to inform eligibility. For the HC subjects, the Visual Interpretation Report will not be provided to the site since it does not impact eligibility.

- If the Visual Interpretation read for a PD subject indicates that the scan does not show evidence of DAT deficit, the subject will not be eligible for participation.
- In addition, a quantitative analysis will be completed to be compared with the  $\alpha$ -syn biomarkers in the biofluid and tissue analyses.

Since this imaging information and the products used to complete the DAT SPECT scans are investigational as used in S4, it cannot provide definite information about a clinical diagnosis.

The procedure for DaTSCAN™ imaging includes:

Women of childbearing potential must have a urine pregnancy test prior to injection of DaTSCANTM. The result must be confirmed as negative prior to proceeding with the injection. Before the DaTSCANTM injection, subjects will be pre-treated with stable iodine (10 drops of a saturated solution of potassium iodide) to reduce the uptake of DaTSCANTM by the thyroid. Subjects will be injected with 3-5 mCi of dopamine transporter. Within a 4 hour (+/- 30 minute) window following the injection, subjects will undergo SPECT imaging on the camera. The data and quality assurance procedures to be employed in this study are described in the S4 Laboratory Manual.

Subjects will be monitored by study personnel for AEs on the day that a DaTSCANTM is obtained. Subjects will also be contacted by phone 7 days (±2 days) following the injection/scan to assess adverse events. These events will be reported by the Site Investigator as required to the site's Institutional Review/Ethics Boards (IRB) and to his/her Radiation Safety Committee.

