# 2. STUDY OBJECTIVES

# 2.1. Primary Objective

The goal of this study is to characterize the distribution of  $\alpha$ -syn pathology through evaluation of quantitative and semi-quantitative outcomes for  $\alpha$ -syn (total, phosphorylated, oligomeric and other  $\alpha$ -syn species) in multiple tissues and body fluids in individual subjects with clinically typical PD and HC. The primary objectives for this study are as follows:

- To evaluate the  $\alpha$ -syn markers as potential surrogate markers for patient selection/enrichment that would be useful in future clinical trials.
- To compare  $\alpha$ -syn load in the biofluids and tissues in PD subjects with HC subjects

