# 3. STUDY DESIGN

# 3.1. Overall Study Design

This is a multi-center, cross-sectional, observational study to evaluate  $\alpha$ -syn pathology in multiple tissues and biofluids in individual subjects with PD and HC at a single time point. Each subject's participation will be approximately 16 weeks. The total duration for sample collection for this study will be approximately 24 months. Analysis of the samples will occur following collection of the samples.

The study is designed to occur in four visits: Screening Visit, Biofluid Collection and Skin Biopsy Visit, Colon Biopsy Visit and Submandibular Gland Biopsy Visit.

The Screening Visit will include obtaining informed consent prior to the initiation of any procedures followed by procedures to evaluate eligibility (clinical laboratory evaluations, medical history, physical examination, electrocardiography [ECG] and DaTSCAN™ Imaging) for participation, Montreal Cognitive Assessment (MoCA) and clinical characterization of PD (Movement Disorder Society Unified Parkinson's Disease Rating Scale [MDS-UPDRS], Hoehn and Yahr, Schwab and England, SCOPA-AUT). In addition, all subjects will complete a University of Pennsylvania Smell Identification Test (UPSIT). DaTSCAN™ imaging obtained as part of the Parkinson's Progression Markers Initiative (PPMI) study may be utilized for this study if completed within 6 months of the screening visit.

Upon confirmation of eligibility and within 120 days of the Screening Visit (based on the date of initial screening activities if occurs on more than one day), subjects will undergo the remaining visits: Biofluid Collection and Skin Biopsy Visit, Colon Biopsy Visit and Submandibular Gland Biopsy Visit. These visits may occur in an order most convenient for scheduling purposes.

For the Biofluid Collection and Skin Biopsy Visit, subjects will undergo collection of whole blood, serum, and plasma for the level of total  $\alpha$ -syn,  $\alpha$ -syn species and other potential biomarkers. Whole blood sample will also be used for extraction of DNA for genomic analyses and RNA for gene expression analyses. Whole blood sample will also be used for a complete blood count (CBC) and assessment of reticulocytes at a central laboratory. Saliva samples will be obtained using the passive drool collection method and analyzed for  $\alpha$ -syn species levels using

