# **3.3.** Study Population

## 3.3.1. Subject Numbers

Up to 100 subjects will be enrolled in this study. Subjects are considered enrolled in the study if they complete screening and are found to be eligible based on the inclusion and exclusion criteria. The enrollment goal for this study is 80 subjects (20 early PD not requiring dopamine replacement therapy, 20 moderate PD on dopamine replacement therapy without motor fluctuations, 20 advanced PD with motor fluctuations, 20 HC subjects) that complete at least 2 biofluid samplings (blood, saliva and CSF) and at least 2 tissue samplings (skin, colon, submandibular gland).

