## 3.3.2. Inclusion Criteria for PD Subjects

• Male or female age 40 or older at the time of PD diagnosis.

- Clinical diagnosis of PD based on bradykinesia plus one of the following: rest tremor or rigidity.
- DAT deficit at screening based on visual interpretation of DaTSCANTM imaging.
- PD subjects will need to fall into one of the following stages:
  - Early untreated PD not requiring dopamine replacement medication (anticholinergics, MAO-B inhibitors and amantadine permitted), Hoehn and Yahr 1-2, < 2 years from diagnosis.
  - Moderate PD responsive and currently treated with dopamine replacement therapy without evidence of motor fluctuations or dyskinesias.
  - Advanced PD with motor fluctuations or dyskinesias, > 5 years from diagnosis.
- Ability to provide written informed consent in accordance with Good Clinical Practice (GCP), International Conference on Harmonization (ICH), and local regulations.
- Willing and able to comply with scheduled visits, required study procedures and laboratory tests.

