## 3.3.5. Exclusion Criteria for PD Subjects

- Has other significant neurological disorders (clinically significant stroke, brain tumor, hydrocephalus, epilepsy, other neurodegenerative disorders, encephalitis, repeated head trauma, polyneuropathy).
- Has significant autonomic dysfunction (symptomatic orthostasis, hypotension or urinary incontinence) suggestive of an atypical parkinsonism.
- Has atypical features of parkinsonism including but not limited to supranuclear gaze palsy, early recurrent falls, corticospinal track abnormalities, cerebellar abnormalities, significant cognitive dysfunction.

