# 3.5. Replacement of Subjects

Subjects that fail the screening procedures will be replaced. The data for this study is most valuable in subjects that have multiple biofluids and tissues for comparison. Up to 100 subjects will be enrolled in this study. The goal of the study is to enroll at least 80 subjects who are evaluable – defined as completing at least 2 biofluid samplings (blood, saliva, and CSF) and at least 2 tissue samplings (skin, colon, submandibular gland).

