### **10.2.** Descriptive Statistics

Descriptive statistics will be generated for important demographic (age, gender, race, ethnicity) and clinical characteristics (duration of disease, MDS-UPDRS total and motor score, Hoehn and Yahr, Schwab and England, MOCA, SCOPA-AUT). For continuous variables, the mean, standard deviation, median, minimum, and maximum will be displayed for each subset of the PD cohort (20 early PD not requiring dopamine replacement therapy, 20 moderate PD on dopamine replacement therapy without motor fluctuations, 20 advanced PD with motor fluctuations), the PD subjects overall, and the HC cohort. For categorical variables, the percentage of subjects falling in each category will be displayed for each of these groups. Comparisons across the groups will be performed using t-tests and/or chi-square tests, as appropriate.

Demographic variables of screen failure subjects, and reasons for screen failures, will be summarized for all subjects who are screened but not randomized into the study.

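### Section 10.4.1 judges the selection/enrichment objective by lowest variability, which does not measure selection, and the groups sampled limit any such conclusion to clinically typical, DAT-deficient PD

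*Protocol*

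**What the plan says.** **Objective.** Section 2.1, the Synopsis and section 10.4.1 give as the first primary objective the evaluation of α-syn markers "as potential surrogate markers for patient selection/enrichment that would be useful in future clinical trials". Neither selection nor enrichment is defined.

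**Analysis.** Section 10.4.1 handles this objective by examining the distribution and the variability of each measurement. It would recommend the one that varies least, because that one needs the fewest subjects. The comparisons of PD with healthy controls (HC) belong to the second primary objective.

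**Outcomes.** For skin, submandibular gland and colon, sections 10.3.2 to 10.3.4 give a positive/negative result as the first form of the outcome. Section 10.3.1 expresses the biofluids as concentrations or ratios, with no cut-off.

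**Who is sampled.** Section 3.3.2 requires "DAT deficit at screening based on visual interpretation of DaTSCAN" for PD subjects. Section 5.1.8 adds that if "the scan does not show evidence of DAT deficit, the subject will not be eligible for participation". Section 3.3.5 excludes anyone to whom this applies: "Has atypical features of parkinsonism including but not limited to supranuclear gaze palsy". Sampling comes "Upon confirmation of eligibility and within 120 days of the Screening Visit" (section 3.1), and section 3.5 says "Subjects that fail the screening procedures will be replaced". The only comparator is a group of 20 HC, whose scan result does not affect their eligibility (section 5.1.8).

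**The concern.** The question and the yardstick do not match. A selection marker is useful if it divides candidates into those to take and those to leave, and if the division means something. Low variability is a virtue in an outcome measure, where it reduces the sample size of a later trial. For a positive/negative marker it can be a fault: a marker that gives almost everyone the same answer varies least and selects least.

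The reach of the objective is also left open. All sampled PD subjects have typical disease and a DAT deficit. A general statement on patient selection would therefore go further than the groups allow unless the population is named.

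At stake is the recommendation that the protocol promises from its first-listed primary objective. As written, it could point to the wrong tissue or fluid for selecting patients, or be applied to patients unlike those studied.

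**Working it through.** The plan states no figure on this point, so there is none to reproduce. The check follows the population through the text and then tests the criterion.

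**1. Population.** Inputs: sections 3.1, 3.3.1, 3.3.2, 3.3.5, 3.5, 5.1.8 and 10.2.
- PD entry needs a DAT deficit; without one the candidate is ineligible.
- Section 3.3.1 defines enrolment by eligibility: "Subjects are considered enrolled in the study if they complete screening and are found to be eligible". Sampling follows eligibility.
- For screen failures, section 10.2 plans only demographics and reasons.
- Clinically diagnosed PD subjects without a DAT deficit who are sampled: 0. The goal is 3 × 20 = 60 DAT-deficient typical PD and 20 HC.

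**2. The criterion.** A positive/negative marker with positivity p has variance p(1−p). The positivities are illustrations, not trial data.
- p = 0.50: 0.50 × 0.50 = 0.25
- p = 0.90: 0.90 × 0.10 = 0.09
- p = 0.95: 0.95 × 0.05 = 0.0475
- p = 0.05: 0.05 × 0.95 = 0.0475
- p = 1 or 0: 0

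Take two hypothetical markers. Marker A is positive in 57/60 PD and 19/20 HC, so p = 0.95 and the variance is 0.0475 in each group. Marker B is positive in 54/60 PD and 2/20 HC, so p = 0.90 and 0.10 and the variance is 0.09 in each group. Lowest variability prefers A, which does not separate PD from HC at all (95% against 95%), over B (90% against 10%).

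**3. What S4 can estimate for selection.** The marker-negative share of DAT-deficient typical PD, with Clopper-Pearson 95% intervals, assuming 10% negative for illustration:
- All PD: 6/60 = 10% (3.8% to 20.5%)
- One stage: 2/20 = 10% (1.2% to 31.7%)

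For HC:
- 20/20 negative: lower 95% limit for specificity 0.025^(1/20) = 83.2%
- 18/20 negative: 90% (68.3% to 98.8%)

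**4. What S4 cannot estimate.** Let f be the share of clinically diagnosed candidates without a DAT deficit, s the positivity in DAT-deficient PD, and q the positivity in the remainder. The DAT-deficient share among marker-positive candidates is (1−f)s / [(1−f)s + fq]. The protocol gives none of these. Assume s = 0.90 and f = 5%, 15% or 20%. S4 samples nobody who informs q, so q runs from 1 to 0:
- f = 5%: 0.855/0.905 = 94.5%, up to 100%; without a marker 95%
- f = 15%: 0.765/0.915 = 83.6%, up to 100%; without a marker 85%
- f = 20%: 0.72/0.92 = 78.3%, up to 100%; without a marker 80%

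The width comes from leaving q unknown. It marks the limit of the design and does not show an error in it. Because section 5.1.8 says that the imaging cannot settle the diagnosis, the share describes DAT status, not true PD.

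**The case against.** **Much of what is wanted is already there.** The distribution of a positive/negative measure is its positive and negative proportions, and these tissue outcomes are defined. Intervals, table layout and biofluid cut-offs can be left to an SAP. This stands: their absence is no finding. What remains is that the protocol itself names the basis for the recommendation, and that basis is variability.

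**Variability is tied to detecting effects of interest, so a sensible analyst would weigh it against effect size.** This is fair, but it is still a criterion for an outcome measure. It does not say whom a marker would select.

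**The restriction to typical, DAT-confirmed PD is stated openly in an exploratory study of potential markers.** This stands in full. It is a reasonable choice and contradicts nothing.

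**Stronger readings a reader might infer.**
- *That S4 has no data on the patients a marker would have to screen out.* The protocol never says the marker must remove patients without a DAT deficit. Selection within DAT-deficient PD fits sections 1.2 and 2.1 equally well, and marker-negative PD subjects are sampled.
- *That S4 data would fit a useless marker as well as a perfect one.* S4 can reject a marker that is often positive in HC or seldom positive in PD. Section 1.1 treats positivity in controls as an open question for colon and submandibular gland.
- *That PD-HC separation will be reported as enrichment, or that a marker will replace DAT imaging.* Neither is planned. Section 10.4.1 keeps the two objectives apart.

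**Conclusion.** The point holds in a limited form. The criterion that section 10.4.1 attaches to the first primary objective does not measure what that objective asks. For positive/negative markers it can rank them the wrong way round: in the illustration, a marker with no PD-HC separation (variance 0.0475) is preferred to one with 90% against 10% positivity (variance 0.09). This rests on the algebra of p(1−p) and on reading the sentence in 10.4.1 as written. The positivities are hypothetical.

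The scope is bounded as well. S4 can inform selection within clinically typical, DAT-deficient PD and the contrast with healthy people. It cannot inform selection among clinically diagnosed patients of uncertain DAT status, because it samples none without a deficit. The 78.3% to 100% range and its companions illustrate that limit under assumed f and s, and are not evidence of a fault. The correction is cheap and better answers the stated question, so it should be made.

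**What to change.** Leave eligibility unchanged.

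1. In section 10.4.1, replace lowest variability as the criterion for the first primary objective. Use the proportions of marker-positive and marker-negative PD subjects for each marker with a positive/negative definition: the tissue measures of sections 10.3.2 to 10.3.4 now, and biofluid measures once a cut-off is set. Give them overall and by stage, with exact 95% confidence intervals and HC positivity alongside. Variability can stay as a description of each measure and as information for future outcome measures.
2. In the Synopsis, section 2.1 and section 10.4.1, state that conclusions on selection apply to clinically typical, DAT-deficient PD.

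The cost is protocol wording, one more table and a narrower claim. No new subjects or procedures are needed. At 20 per stage the intervals will be wide (1.2% to 31.7% for 2 of 20), so the stage-specific figures will be descriptive.

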### 5.1.9. Blood Sampling

Whole blood (about 6 ml), serum (about 10 ml) and plasma (about 10 ml) will be collected to quantify total  $\alpha$ -syn and  $\alpha$ -syn species and also enable further exploratory biomarker analyses. An additional EDTA blood sample will be obtained (about 6 ml) for the extraction of DNA to conduct sequencing and genomic analyses. Blood will also be collected in PaxGene tubes (about 10 ml) for the extraction of RNA to conduct gene expression analyses. Additional blood (about 4 ml) will be collected to analyze CBC and reticulocyte counts. This additional blood for CBC and reticulocyte should be obtained on the same day or within 1-2 days of the research blood sampling. It is strongly advised that the research blood samples are collected in a fasted state (i.e., minimum of 8 hours since last meal/food intake) to ensure the quality of samples for future analyses. If fasting is not possible, then subjects should be strongly advised to eat a low lipid diet as provided. All research samples will be collected as described in the S4 Laboratory manual and sent to a central biorepository for analysis of blood cell counts for research purposes or to be stored for analysis of  $\alpha$ -syn species. Samples will be made available to researchers with expertise in  $\alpha$ -syn assays to conduct these analyses. Remaining samples may be used to evaluate other proteins, analytes or potential biomarkers. Subjects will not receive any individual results of analysis or testing conducted on the blood samples.

### 5.1.10. Lumbar Puncture

LP for CSF collection should be performed in the morning between 8-10am, preferably in a fasted state. If fasting is not feasible, then a low fat meal should be followed. The LP is performed by the Site Investigator or another qualified clinician appointed by the Site Investigator. An LP for the collection of 15-20 ml of CSF will be conducted for all subjects enrolled in the study. Prior to performing the LP, the Site Investigator will review the laboratory values to ensure that there is no evidence for a coagulopathy or other risk for bleeding. A fundoscopic examination or review of recent brain imaging will be performed to exclude conditions of increased intracranial pressure prior to performing the LP. The recommended procedure for performing the LP and collection of CSF is provided in the S4 Laboratory Manual. If difficulties obtaining spinal fluid occur and the subject is willing, an LP may be performed supported by fluoroscopy or ultrasound on the same or another day. The first 2 ml of CSF will be processed at the site's local lab facility to conduct standard analyses on white and red blood cell count, and total protein level. The remaining volume of CSF will be processed following the S4 Laboratory Manual and sent frozen to a central biorepository for storage. Samples will be made available to researchers with expertise in analysis of  $\alpha$ -syn and/or other biomarker. Remaining samples may be used to evaluate other proteins, analytes or potential biomarkers. Subjects will be closely monitored during the procedure and following the procedure. Subjects will be contacted by phone  $7 \pm 2$  days following an LP to assess for any AEs. Subjects will not receive any individual results of analysis or testing conducted on the CSF samples.

